Exploratory Aim 1) To study genetic variation as a predictor of treatment response to ZNS using a convergent functional pharmacogenomics approach. This will be based largely on information gleaned from genomic analysis that has already been performed, although we will also perform a meta-analysis on data and samples on hand from previous clinical trials that are already completed. Those samples from previous studies will be genotyped using genome-wide assay, and merged with de-identified clinical trial data, consisting of items such as responses to assessments, demographics and other data collected during study visits (See section 6.E through 6.K for information on study visits) which may be pertinent to the overall study (all data and samples are de-identified) at Yale University. That data will be analyzed (in de-identified fashion) at both VCU and at Yale. VCU will host their own version of REDCap which may be used to store the data. Those findings will be used to generate methods of predicting outcomes and medication response in the ZNS trial data. All the ZNS trial subjects will be genotyped with

V.6 05Jun2020 1

a genome-wide assay. We hypothesize that we can predict the response to medication based largely on a genetic risk prediction score (GRPS) generated from an empirically derived set of polymorphisms in genes known to be involved in the pathophysiology of AUDs and a stress-reactive endophenotype. We hypothesize that the ZNS treatment effect compared with placebo will be greater for subjects with higher GRPS in terms of reduced drinking. We will develop and refine this method in an available discovery samples from clinical trials of AUD via meta-analysis before testing it in the ZNS samples.

Exploratory Aim 2) To compare ZNS and placebo-treated subjects on pre- and post-treatment changes in measures of stress-reactivity (i.e., stress-induced anxiety, alcohol craving, autonomic nervous system activity), cue-elicited craving, and impulsivity. We hypothesize that ZNS will attenuate stress-reactivity, cue-elicited craving, and impulsivity more than placebo in a stress laboratory paradigm, and that attenuation of those measures will be associated with reduction in drinking.

4. BACKGROUND:

4. A. Alcohol Use Disorders Background.

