An important initial consideration in considering efficacy will be to identify baseline differences between groups that may have occurred despite randomization. A successful outcome during the treatment trial will be defined in terms of a statistically significant difference on the primary outcome measure: drinks per week, compared during the 8 weeks of active treatment at the target dose, allowing for an 8 week grace period for the medication titration. For all analyses, heavy drinking days will be defined as follows; for men > 4 drinks in a day and for women > 3 drinks in a day. Patients will be followed irrespective of whether they continue to receive medication treatment, so that analysis will include all data available for the 8-week treatment period. All analyses will be **intent-to-treat**. The α will be set at .05 for the primary outcome variable. Between site differences will be explored. We will test interaction effects of GRPS in the regression models for the primary/secondary outcomes (**Exploratory Aim 1**), testing the hypothesis that ZNS's effect on drinking is greater in those with higher GRPS.

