- 6. K. 4. To use telephone-based daily process data collection to elucidate the mechanism of action of ZNS as it relates to changes in craving, anxiety, self-efficacy, and genetic variation (Specific Aim 2, Exploratory Aim 1): Multilevel models will be used to evaluate the associations between craving, self-efficacy, anxiety, and daily drinking and how these associations vary as a function of medication group and GRPS. Similar to [name] et al. [79], we will focus on predicting nighttime drinking (i.e., drinks consumed after the early evening report), but here we will use psychological measures reported during the early evening in the daily survey. Nighttime drinking levels will be determined by subtracting the number of drinks consumed during the current day from the total number of drinks consumed for that day (reported the following day). We will follow the general analysis scheme used by [name] et al. [79], but will use mixed effects/multilevel models, rather than generalized estimating equations (GEE) models [99] because mixed models give unbiased estimates under less restrictive assumptions about missing data. We will examine the number of drinks consumed (using a Poisson model or negative binomial model if there is overdispersion). We will use the HGLM module of the HLM7 program, as it is more flexible for some of our models than PROC GLIMMIX in SAS. Analysis will focus on the last eight weeks of treatment, consistent with the analyses of outcomes in Aim 1. We will test the hypothesis that ZNS reduces nighttime drinking and that craving, anxiety, and GRPS act as moderators of this effect. We anticipate greater ZNS effect in subjects with greater anxiety, craving and genetic loading (greater GPRS). We will examine whether ZNS's effect on drinking is mediated by self-efficacy using the approach of Kraemer et al. [100, 101], such that self-efficacy is significantly affected by ZNS treatment, and has a main or interaction effect on nighttime drinking in the model containing both treatment and the potential mediator as predictors.
- 6. K. 5. Stress Reactivity Lab (Exploratory Aim 2): We will compare pre- and post-treatment changes in levels of anxiety, craving, and impulsivity measures induced by stressful and alcohol-cue imagery in the lab. We will test if the mean induced changes are attenuated by ZNS more than placebo using ANCOVA. The amount of reactivity pre-treatment will be explored as a covariate in secondary outcome models.

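### Section 6.K.4 predicts a larger zonisamide effect in subjects with greater craving and anxiety, but names only on-treatment daily ratings of both and plans no treatment x baseline AUQ or STAI term

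*Combined protocol and SAP*

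**What the plan says.** Section 6.K.4 sets a moderation hypothesis, "We will test the hypothesis that ZNS reduces nighttime drinking and that craving, anxiety, and GRPS act as moderators of this effect", and then gives its direction: "We anticipate greater ZNS effect in subjects with greater anxiety, craving and genetic loading". Specific Aim 2 (section 3) also names craving, anxiety and genetic variation as moderators, with self-efficacy as the mediator.

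- **Measures.** For craving and anxiety, 6.K.4 says "here we will use psychological measures reported during the early evening in the daily survey".
- **Window.** "Analysis will focus on the last eight weeks of treatment, consistent with the analyses of outcomes in Aim 1".
- **No pre-treatment daily series.** IVR training is at the baseline visit (6.E.2), medication starts the same day (6.E.4), IVR payment covers 16 weeks (6.G.6), and Table 2 shows IVR reports from week 1.
- **Expected drug effect on the ratings.** Section 4.A states that ZNS lowers both anxiety and craving. The 6.K.4 heading sets out to "elucidate the mechanism of action of ZNS as it relates to changes in craving, anxiety, self-efficacy, and genetic variation". Exploratory Aim 2 expects that "attenuation of those measures will be associated with reduction in drinking". AUQ is a secondary outcome in 6.K.2.
- **Planned interactions with pre-treatment characteristics.** For the genetic score, 6.K.1.a says "We will test interaction effects of GRPS in the regression models for the primary/secondary outcomes". For craving and anxiety there is none. The nearest item is stress-lab reactivity in 6.K.5: "The amount of reactivity pre-treatment will be explored as a covariate in secondary outcome models". No interaction with treatment is stated there, and 6.E.3 lets subjects skip the lab.

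**The concern.** The prediction compares kinds of subject: those with more craving or anxiety should gain more from ZNS. A dependable test needs a characteristic that treatment cannot have altered. The ratings named in 6.K.4 are made after at least half of the treatment period, and the protocol expects the drug to change them. Comparing arms at the same on-treatment craving therefore compares subjects who may have differed before treatment.

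If the daily rating enters unsplit, the term also mixes day-to-day swings within a person with differences between persons. Section 6.K.4 does not say which value enters the moderator term or how it is centred.

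At stake is the reading of one Specific Aim 2 hypothesis. A null on-treatment interaction could be reported as showing that craving does not identify responders, and a non-zero one as showing that it does. Neither conclusion would be safe.

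**Working it through.** **The plan's own figures.** None applies. Section 6.K.8 says only that medium-to-large effects can be detected. The 6.K.7 figure (N=128, d=0.5, power above 0.80) reproduces at 0.80-0.81 but concerns the main effect of group.

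**Algebra.** Let c be untreated craving in SD units, s the slope of log drinks on craving, and k the factor by which ZNS shrinks craving. The values of s and k are assumptions; the documents give none.

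1. *Proportional shrinkage, drinking follows.* Log drinks = a + s x actual craving in both arms, and ZNS moves c to kc + constant. The ZNS effect for a subject is then a constant minus s(1-k)c.
   - k=0.7, s=0.3: -0.3 x 0.3 = -0.09 per SD, a rate-ratio multiplier of 0.91.
   - k=0.5, s=0.5: -0.5 x 0.5 = -0.25 per SD, a multiplier of 0.78.
   - At equal on-treatment craving the arms differ by a constant, so the on-treatment interaction is 0 for any s, k or N.
   - A baseline score with reliability 0.8 and correlation rho with later craving has coefficient -s(1-k) x rho x sqrt(0.8). For (k, s, rho) = (0.7, 0.3, 0.6), (0.5, 0.5, 0.6) and (0.5, 0.5, 0.8) this is -0.048, -0.134 and -0.179.
2. *Ratings compressed, drinking does not follow.* Log drinks depend on c in both arms, but the ZNS rating is kc + constant. The slope on the rating is s/k under ZNS and s under placebo. The interaction is s(1/k - 1) with no true moderation: 0.3 x 0.43 = 0.13, or 0.5 x 1 = 0.50.
3. *Uniform fall of d.* T x (c - d) = T x c - dT. Only the main effect moves; the interaction is unchanged.

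**Simulation.** Assumptions: 1000 replicates per cell; 56 days with 82% of calls completed (6.G.6 cites 81.6% and 83.5%); overdispersed Poisson random-intercept model with cluster-robust standard errors; within-person craving SD 0.8; random-intercept variance 0.5. The 64 per arm comes from N=128 in 6.K.7. The 128 per arm is 160 per arm less 20%, for the potential N=320 in section 3.

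Percent significant at 0.05, 64 per arm then 128 per arm:

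| True state | Unsplit daily | On-treatment person mean | Baseline score |
|---|---|---|---|
| Proportional shrinkage (item 1) | 5-6, then 5-7 | 5-6, then 5-7 | 8-28, then 10-44 |
| Moderation by baseline craving, x0.67 per SD, ratings unchanged | 7-9, then 10-12 | 42-67, then 69-91 | 75, then 95-97 |
| Same, x0.82 per SD | 7, then 6-7 | 16-25, then 25-40 | 28-29, then 49-51 |
| Moderation by concurrent untreated craving, x0.67 per SD, ratings unchanged | 12-13, then 13-17 | 85, then 99 | 32-58, then 65-86 |

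With no moderation, with or without a uniform 0.5 SD fall in ratings, all tests reject in 4-8%.

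Two further checks used simpler subject-level models:

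- *Compressed ratings, drinking not following (item 2).* The on-treatment term was falsely significant in 16-86%, against 7-8% for the baseline term.
- *Concurrent-craving moderation with lowered ratings* (64 per arm, s=0.3, rho=0.6, x0.67 per SD, 600 replicates). Person mean against baseline: 80% v 38% with ratings unchanged, 82% v 37% with a uniform 0.5 SD fall, 91% v 49% with a 30% proportional fall.

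**Precision of a baseline interaction.** With SE = 2 x SD/sqrt(N), the interaction detectable at 80% power is (1.96 + 0.84) x 2/sqrt(128) = 0.50 outcome SD per SD of moderator at N=128, and 0.35 at N=256.

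**The case against.** The strongest case for the plan has four parts.

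*The daily analysis asks a legitimate question.* Section 6.K.4 opens by asking how the associations vary by medication group, and 6.G.6.b presents the IVR data as a means of testing moderation day by day. This stands, and the daily models should stay.

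*The plan is silent rather than wrong.* Section 6.K.4 does not say which craving value enters the term, and it follows the scheme of a cited naltrexone study that is not available here. A baseline value is not excluded. This also stands, but it is a reason to specify the term.

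*The harm depends on the mechanism.* A reader might infer that the protocol's own premise forces the on-treatment interaction to zero. The documents do not support that. They expect craving to fall and link its attenuation to drinking, but they name self-efficacy as the mediator and nowhere say that the fall is proportional or carries the whole effect. A reader might also infer that the person mean is the better test only if ZNS leaves ratings untouched. That is wrong: a uniform fall does not bias the interaction, and if concurrent untreated craving is the true moderator, the person mean remains more sensitive when ratings are lowered.

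*The remedy is weak.* Under proportional shrinkage the baseline term is significant in only 8-28% at 64 per arm. The 128 per arm is an upper bound, because 6.B makes the IVR component optional for Richmond veterans. Two exploratory tests are added. All of this stands and limits what the baseline terms can show.

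**Conclusion.** The concern holds as a gap between a subject-level prediction and the measures named to test it. On-treatment ratings can validly describe how the craving-drinking and anxiety-drinking associations differ by arm. They are not a reliable test of who benefits, because the interaction can be zero with real moderation or non-zero with none, depending on how ZNS changes the ratings and whether drinking follows. It would go too far to call the on-treatment analysis invalid or insensitive in general: under no moderation with a uniform fall it rejects at about the nominal rate, and in some settings it is the stronger test.

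All sizes rest on assumed slopes, correlations and reliability. The textual finding does not: the documents name on-treatment IVR ratings, schedule no pre-treatment series, and plan an interaction for GRPS but not for baseline AUQ or STAI. This is a cheap improvement to an exploratory analysis. The primary outcome is unaffected.

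**What to change.** In 6.K.4:

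- Add treatment x baseline AUQ and treatment x baseline STAI as the test of the subject-level prediction. Label both exploratory and report estimates with confidence intervals.
- Keep the daily treatment x craving and treatment x anxiety terms, each split into person mean and daily deviation. State that they describe mechanism and will not be read as showing who benefits.
- Leave treatment x GRPS and the self-efficacy mediation test as they are.

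The cost is SAP wording, settled before outcome data are examined by arm. No new data are needed: Table 2 marks AUQ at baseline, and 6.G.5.e has STAI at each visit (its row in Table 2 is not legible in the extracted text). The downside is two more exploratory tests on a single, coarser score, with about 28-29% power at 64 per arm and at most 49-51% at 128 per arm for a multiplier of 0.82 per SD. The SAP should therefore say that a null baseline term is not evidence that craving or anxiety is irrelevant to benefit.

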Title: Zonisamide Treatment of Alcohol Use Disorder: an Evaluation of Efficacy and Mechanism of Action

NCT #: NCT02900352

Document date: June 5, 2020

Document Type: Protocol and Statistical Analysis Plan

1. Principal Investigator: [name]., M.S.

2. Project Title:

"Zonisamide treatment of Alcohol Use Disorder: an evaluation of efficacy and mechanism of action"

3. Purpose, hypothesis and key questions

Purpose: To comprehensively evaluate the efficacy of an anticonvulsant medication zonisamide (ZNS) for the treatment of alcohol dependence in civilians. We want to see if the medication works to reduce harmful drinking patterns, and try to determine whether medication response can be predicted by a few key factors such as genotype, the age of onset of alcoholism (early vs. late), or stress-reactivity. This protocol also contains translational substudies that will help elucidate the mechanism of action of the medication and determine subject characteristics that predict preferential response.

SPECIFIC AIMS: Zonisamide (ZNS) is an anticonvulsant medication for which evidence of efficacy in treating alcohol use disorders (AUDs) was obtained in two small placebo-controlled pilot studies. We propose to 1) add a civilian arm (N=160) to complement the existing VA/CSR&D study comparing ZNS to placebo over 16 weeks of treatment; 2) add important mechanistic and translational components to both trials (potential N=320) to elucidate the mechanism of action of ZNS and enhance our understanding of how anticonvulsant treatments reduce drinking. Importantly, there is no overlap between the VA/CSR&D funding, and the proposed NIH funding. So we will evaluate *efficacy*, *safety*, *and mechanism of action* of zonisamide in treating alcoholism.

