either ZNS (80 subjects) or PLC (80 subjects). Note that the translational sub-studies (genetics, and stress reactivity lab) will be performed on both the civilians and veterans, so they will occur at all 4 total sites for both the civilian and veterans studies: VA Connecticut (the West Haven VAMC), UCONN Health Center, VCU IDAS, and the RichmondVAMC. We anticipate an upper limit of enrollment to be N=200, however for the study we have a participant target goal of N=160. For the sake of simplicity, we describe those procedures here written for the civilians only, but they will be added separately to the veterans study protocol also. The funding for the translational sub-studies will come from NIAAA. We would like to reserve the right to enroll veterans here at VCU IDAS for the translational components of the study only, if that is easier logistically than running the translational components at the Richmond VAMC. The Richmond VAMC will recruit veterans for the study, using their specialized protocol and these participants will be given the option of coming to VCU for the add-on stress lab and IVR components.

6.C. Clinical Trial Inclusion and Exclusion Criteria:

Participants: N=160 men and women **civilians** from the greater Richmond area are being recruited through radio, bus, and print advertising, online advertising, study web sites, referrals, and flyers at VCU facilities and community areas (i.e., coffee shops, grocery stores, etc.), as well as surrounding area clinics. We will also utilize HM20000294 in which participants indicated if they would like to be contacted for future studies in order to identify and contact potential participants

Inclusion Criteria (each subject must meet all of the following to participate): a) age 21-70 years, inclusive; b) regular heavy drinkers as defined by averaging ≥ 2 heavy drinking days per week over the 90 days baseline pre-treatment timeline follow-back (TLFB), and *current DSM-5 AUD* that recognize a need to reduce or stop drinking; c) willingness to provide written, informed consent to participate in the study; and d) for women of child-bearing potential (i.e., no hysterectomy, bilateral oophorectomy, or tubal ligation or <2 years postmenopausal), must be non-lactating, practicing a reliable method of birth control, and have a negative serum pregnancy test prior to initiation of treatment. Section 6.I reviews medications allowed and not allowed during study.

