- **6.K. 6. Safety:** Safety will be analyzed using categorical outcomes, defined by the type and severity of adverse effects. Summary measures of adverse events will be developed by organ system from the SAFTEE [77, 78] and will be compared for patients receiving ZNS or PLC using \Box^2 analysis or Fisher's exact tests, with an emphasis on moderate-to-severe adverse events.
- 6. K. 7. Sample Size And Power Estimate (Specific Aim 1): For continuous outcomes, based on the effect sizes from our pilot study of ZNS (showing a moderate effect size on drinks/week d=0.5, and .27 HDD/week), we estimated that a study with N=128 subjects (a 20% drop out rate) would be well powered (>.80) to detect a medium effect size difference on the secondary outcomes HDD per week and total drinks per week for the main effect of group assuming alpha level of 0.05. Based on past trials we are expecting a dropout rate < 30%. We will quantitatively examine the veteran and civilian populations for differences in variance and treatment response, and combine them (if valid) in a patient-level pooled analysis, further increasing power on all outcomes. If substantial differences are observed between the veteran and civilian samples, we will meta-analyze them. For PSNHDD, from the pilot study, in the ZNS group, 12 of 20 subjects did not relapse in the 28 days of the study, compared to 7 of 20 PLC subjects. Using this effect size, the proposed sample size of 80 subjects per group has >89% power to detect such a difference in the rates of no heavy drinking (i.e. 60% vs. 35%), assuming a two-sided alpha level of 0.05. We can also detect slightly smaller differences (60% vs. 38%, 35% vs. 57%) with 80% power under the same assumptions. Both in the estimation of effect

size from the pilot data and in the sample size analysis, dropouts are counted as relapsed to heavy drinking.

6 K. 8. Pharmacogenomic and Micro-longitudinal analyses power estimate (Aim 2, exploratory aims): There is little ZNS-specific data by which we could reasonably estimate effect sizes for these analyses. Three recent treatment studies by our group showed significant pharmacogenetic effects with samples of about 110-150 in each [15, 85, 102]. By using a mixed models approach on drinking variables, and HLM for the micro-longitudinal analyses, we will be adequately powered to detect medium-to-large effects in these analyses.

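### Section 6.K.6 compares safety by significance tests alone, and at 80 per arm those tests usually miss a doubling of an uncommon adverse event; report risk differences with intervals

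*Combined protocol and SAP*

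**What the plan says.** Section 3 (Specific Aims) lists safety beside efficacy and mechanism of action as something the trial will assess (the sentence opening "So we will evaluate").

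The between-arm safety analysis is in section 6.K.6: "Safety will be analyzed using categorical outcomes, defined by the type and severity of adverse effects". It continues: "Summary measures of adverse events will be developed by organ system from the SAFTEE", and these summaries are compared between the arms by chi-square "analysis or Fisher's exact tests, with an emphasis on moderate-to-severe adverse events". The section gives no expected event rates, alpha, effect measure, interval, margin or detectable difference.

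Section 6.B sets the group sizes: "either ZNS (80 subjects) or PLC (80 subjects". Section 6.K.7 justifies that size on drinking outcomes. Its only power figure for a binary outcome is for efficacy: "the proposed sample size of 80 subjects per group has >89% power to detect such a difference in the rates of no heavy drinking", at 60% vs 35%, "assuming a two-sided alpha level of 0.05". The same section foresees pooling civilians with veterans if that proves valid, and meta-analysis otherwise.

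**The concern.** A test answers whether the arms differ detectably. It does not say how large an excess of harm the data still allow. With a stated interest in safety and only tests planned, a table of non-significant p values would be the whole result for most organ systems, and it could sit alongside a substantial excess on ZNS.

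The stress on moderate-to-severe events sharpens this. Within an organ system, such events cannot be more frequent than events of any severity, so the planned emphasis moves the comparison towards lower rates, where the tests are weakest.

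The background shows how easily small null results become reassurance. Section 4.A.2.b reports no metabolic acidosis and no paresthesias on ZNS in an earlier comparison with 19 ZNS subjects. Zero of 19 leaves a one-sided 95% upper bound of 1 - 0.05^(1/19), about 15%.

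**Working it through.** **Inputs.** From the document: 80 per arm (6.B); two-sided 0.05, stated in 6.K.7 for the no-heavy-drinking outcome and assumed here for safety; potential N=320 with veterans (Section 3), so 320/2 = 160 per arm if allocation is 1:1. Assumed: the placebo event rate p, varied from 5% to 25%, doubled to 2p on ZNS.

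**Step 1: reproduce the plan's own binary power.** Pooled-variance normal approximation:

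power = Φ{ [ |p1 - p2|·√n - 1.96·√(2p̄(1 - p̄)) ] / √(p1(1 - p1) + p2(1 - p2)) }

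For 60% vs 35%, n = 80, p̄ = 0.475: (0.25 × 8.944 - 1.96 × 0.7062) / 0.6837 = 1.246, so power = 89.4%. The plan says above 89%. The two smaller differences ("We can also detect slightly smaller differences (60% vs. 38%, 35% vs. 57%) with 80% power under the same assumptions") give 80.1% and 80.3%. The plan's figures reproduce.

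**Step 2: apply the planned safety tests.** Exact power sums over all 81 × 81 possible tables:

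power = Σi Σj Bin(i; 80, p) · Bin(j; 80, 2p) · 1[test of (i, j) has p ≤ 0.05]

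| Placebo vs ZNS | Fisher | Chi-square (uncorrected) |
|---|---|---|
| 5% vs 10% | 14% | 21% |
| 7.5% vs 15% | 25% | 32% |
| 10% vs 20% | 35% | 42% |
| 15% vs 30% | 56% | 64% |
| 20% vs 40% | 75% | 80% |
| 25% vs 50% | 88% | 91% |

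The normal approximation agrees with the chi-square column. For 10% vs 20%: (0.1 × 8.944 - 1.96 × 0.5050) / 0.5 = -0.191, so 42%.

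Searching over p, power for a doubling passes 50% at a placebo rate of about 12% (chi-square) or 13.5% (Fisher). It reaches 80% at about 20% or 22%.

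**Step 3: pooled with veterans, 160 per arm.** 5% vs 10%: 32% (Fisher) to 39% (chi-square). 10% vs 20%: 66% to 71%.

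**Step 4: a single organ system.** Suppose 8/80 on placebo and 16/80 on ZNS.

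- Chi-square: z = 0.10 / √(0.15 × 0.85 × 2/80) = 1.77, p = 0.08. Fisher p = 0.12. With 8 placebo events, significance needs 18 ZNS events (chi-square) or 19 (Fisher).
- Wilson limits: 12.7% to 30.0% for 16/80; 5.2% to 18.5% for 8/80.
- Newcombe lower limit: 0.10 - √[(0.200 - 0.127)² + (0.185 - 0.100)²] = -0.012.
- Newcombe upper limit: 0.10 + √[(0.300 - 0.200)² + (0.100 - 0.052)²] = 0.212 (unrounded Wilson limits used).

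The test reads as not significant. The interval, -1 to +21 percentage points, shows that an excess of up to 21 points is not excluded.

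**Step 5: width when observed rates are equal.** 1.96·√(2p(1 - p)/80) gives ±6.8 points at 5%, ±9.3 at 10% and ±12.4 at 20%.

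**The case against.** Several points on the other side are sound.

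- **The tests do not fail for every doubling.** A reader might infer from the 10% vs 20% case that the trial would miss most doublings. The document gives no adverse-event rates, so that cannot be said. From a placebo rate of 15% upward, power for a doubling exceeds one half, and a systematic SAFTEE interview could yield such rates for events of any severity. The criticism applies to the uncommon end.
- **The plan does not equate non-significance with safety.** A reader might infer that it does. Section 6.K.6 says only that the arms will be compared, and it sets no safety success rule and claims no safety power. The point is an omission, not a stated error of inference.
- **Dropout.** A reader might assume that dropout lowers these powers further. The document does not support that. Adverse effects are recorded at every visit (6.G.5), patients are followed whether or not they stay on medication (6.K.1.a), and nothing restricts safety to completers, so an event before dropout still counts.
- **Size and oversight.** No aim carries a safety hypothesis, and not sizing a 160-patient efficacy trial on adverse events is ordinary. Laboratory checks, suicidality ratings, neurocognitive tests and six-monthly board review add protection, though none comes with a specified between-arm analysis. Section 6.L points to a Human Subjects appendix that is not part of this document; the statistical plan does not defer its safety analysis to it.
- **Pooling would help.** It is conditional on validity, and 6.K.7 speaks of all outcomes without naming safety. Step 3 shows that it eases the limit without removing it.
- **An interval adds no data.** True, and without a margin it is not a decision rule. What it adds is a visible statement of what has not been ruled out, which a p value does not give.

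**Conclusion.** The point stands in limited form. Section 6.K.6 rests the between-arm safety comparison on tests alone. At 80 per arm those tests miss a doubling more often than they find it when the placebo rate is below about 12% (chi-square) or 13.5% (Fisher), so a non-significant result for an uncommon event says little about harm.

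This rests on assumed event rates, an assumed two-sided 0.05 for safety, and all 80 patients per arm contributing. That moderate-to-severe categories will mostly fall below the threshold is plausible, but the document does not show it. Efficacy conclusions are unaffected. This is a cheap improvement that changes what the trial can say about harm, not a flaw that invalidates the design.

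**What to change.** In 6.K.6:

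1. Make the main safety comparison for each organ system the risk difference (ZNS minus placebo) in the proportion of patients with at least one moderate-to-severe event, with a 95% confidence interval by a method suited to small counts, such as Newcombe.
2. State that the upper limit will be reported as the largest excess the data do not exclude, and that p>0.05 will not be reported as absence of harm.
3. Keep Fisher p values as supporting information.

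The cost is a few lines of SAP text and an extra column in the adverse-event tables, with no new data and no change in conduct. The downside is that the wide intervals become visible (about ±9 points at a 10% event rate), so the safety statements will read less favourably.
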